#### *3.2.4 Phage-Sensitive Intent-to-Treat Population (Efficacy Population 4)*

The Phage-Sensitive ITT Population is defined as all randomized subjects in Phase 1b and Phase 2a who received at least 4 initial doses of study drug, and whose SA isolate is sensitive to at least 1 of the phage components that comprise the study drug.

Phage-Sensitive ITT Population will be reported by the Sponsor separately.

#### *3.2.5 Safety Population*

The Safety Population is defined as all randomized subjects in Phase 1b and Phase 2a who receive at least 1 dose of study drug (ITT population).

#### *3.2.6 Pharmacokinetics Population*

The PK Population is defined as all subjects in Phase 1b and Phase 2a with at least 1 PK sample drawn and analyzed.

The PK analysis will be described by a separate PK Analysis Plan and the PK Population will not be included in this SAP analyses.

### **3.3 Subject Data and Study Conduct**

#### *3.3.1 Subject Disposition*

The following subject disposition categories will be summarized via counts and percentages by Phase and treatment for all randomized subjects:

- Subjects who were randomized
- Subjects who were treated with study drug
- Subjects who completed study treatment
- Subjects with early termination of study drug (count and percentage will be calculated based on subjects who were treated with study drug)
  - Primary reason
- Subjects who completed study
- Subjects who discontinued the study
  - Primary reason

All randomized subject disposition data will be presented in a data listing.

#### *3.3.2 Protocol Deviations*

Counts and percentages of subjects with CSR reportable protocol deviations by deviation category will be summarized by Phase and treatment based on the randomized Population. The definition of CSR reportable protocol deviations is referring to protocol deviation plan.

The protocol deviations will be presented in a data listing based on randomized subjects.

### 3.3.3 Analysis Populations

Counts and percentages of subjects in ITT and Safety populations will be summarized by Phase and treatment based on subjects who were treated with study drug.

Counts and percentages of subjects in Per Protocol MITT population will be summarized by Phase and treatment based on subjects who received at least 4 doses of study drug.

Counts and percentages of subjects in Phage Persistence and Phage Clearance populations will be summarized by Phase and treatment based on subjects who are in Phase 1b Cohort 2 and Phase 2a and received at least 4 doses of study drug.

Counts and percentages of subjects in Phage-sensitive ITT population will be summarized by Phase and treatment based on subjects who received at least 4 doses of study drug and for whom the central laboratory received a blood SA isolate for phage sensitivity testing. Subjects with a blood SA isolate will include all subjects who have blood culture isolates based on blood culture samples from central laboratory (at screening, Day 1 to Day 7, TOC for study drug, TOC for BAT, EOS, or other unscheduled visits).

Reasons for exclusion from Per Protocol MITT and PK Populations will also be summarized.

The analysis population will be presented in a data listing based on randomized subjects.

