7.7 Blood Cultures

Blood cultures and susceptibility testing will be performed by a local microbiology laboratory per the laboratory's standard procedures and standard of care at Screening, daily from Day 1 through Day 7 as indicated in the Schedule of Procedures ([Appendix A](#)). Blood cultures should be collected regardless of clinical indication at Day 1, EOT for study drug (Day 5), Day 7, TOC for study drug (Day 12), TOC for BAT, and EOS. Isolates of SA from positive blood cultures for standard of care blood cultures used to assess eligibility as well as from study cultures will be sent to the central microbiology laboratory for confirmations of identification and susceptibility testing.

Two sets of blood cultures, preferably from 2 different sites, 30 minutes apart will be drawn on Day 1 as close to the start of study drug administration as possible, unless blood cultures have already been sent that day for Screening or clinical care. Thereafter, 1 set of blood cultures is acceptable. Blood cultures should be collected from a peripheral venipuncture site when possible until 2 consecutive days of negative blood cultures are obtained or otherwise as clinically indicated. Repeat blood cultures will also be obtained at EOT for study drug (Day 5), Day 7, each of the TOC (BAT and study drug) and the EOS Visits to evaluate for microbiological cure and sustained cure.

Subjects' SA blood culture isolates will be classified as MSSA or MRSA.

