7.7.1 Criteria for Positive Blood Culture for Eligibility

For study eligibility, subjects must have blood culture positive for SA determined by rapid diagnostic or conventional method from blood culture specimens collected within 72 hours prior to randomization. Time of positive blood culture starts from when specimen is collected for blood culture. The site microbiological laboratory is encouraged to use a Food and Drug Administration (FDA)-cleared, European Conformity-in vitro diagnostic certified, or Sponsor-approved rapid diagnostic test to identify SA if it is available at the site. Subjects may be enrolled based on a positive result from a rapid diagnostic test, but confirmation of SA by conventional culture methods will be the required objective measure for SA in the study analyses for efficacy. Subjects who are enrolled based on a positive rapid diagnostic test, but have negative blood culture result for SA, will discontinue study drug if the Investigator decides to discontinue antibiotic treatment of SAB. In the event subjects will complete the EOT for the study drug safety evaluations and have additional safety follow-up 7 days after last dose in person, if feasible, or by phone.

The study site's local microbiology laboratory will perform identification and in vitro susceptibility testing to standard of care antibiotics according to local practices for all blood cultures positive for SA. The Investigator should ensure that all SA isolates obtained from all cultures performed during the study period (and wherever possible, the isolate from the initial positive culture for SA) are sent to the central microbiology laboratory, as described in the Laboratory Manual. The local microbiology laboratory will be required to prepare SA isolates for shipment to the central microbiology laboratory as outlined in the Laboratory Manual. Although only SA isolates should be sent to the central microbiology laboratory, all organisms isolated from blood cultures performed during the study should be recorded in the electronic data capture (EDC) system. The central microbiology laboratory will confirm the identification and perform in vitro susceptibility testing and phage susceptibility of isolates in batches for the purposes of the final study analysis; the central microbiology laboratory will not be providing results to the sites. Further evaluation to identify the potential mechanism of resistance may be performed.

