9 STATISTICS

9.1 Analysis Populations

The following analysis populations will be defined for the Phase 1b and Phase 2a cohorts:

- Intent-to-Treat (ITT): all randomized subjects regardless of whether or not study drug is received;
- Phage-Sensitive ITT: all randomized subjects who receive both BAT and study drug, and whose SA isolate is sensitive to at least 1 of the phage components that comprise the study drug;
- Safety: all randomized subjects who receive at least 1 dose of study drug;
- MITT: all subjects in the ITT Population with baseline SAB and who receive at least 1 dose of study drug; and
- PK: all subjects (enrolled at predetermined/qualified PK sites) who have at least 1 PK sample drawn.

An SAP will be prepared and finalized before database lock and analyses of data. Summary data will be tabulated and presented by treatment group.

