- TEAEs, which are defined as AEs occurring after the first dose of study drug through TOC for study drug (Day 12) or through EOS for SAEs
- Proportion of subjects with acute kidney injury (AKI), defined as stage 1 or higher using modified Risk-Injury-Failure-Loss-End-stage renal disease (RIFLE) criteria at any time within the first 7 days or new need for renal replacement therapy between Day 1 and EOS
- Vital signs
- Clinical laboratory evaluations
- Change in C-reactive protein (CRP) from baseline to EOS
- Change in interleukin-10 from baseline through TOC for study drug (Day 12)
- Change in SA isolate sensitivity to AP-SA02 between initiation of study drug and the last isolation of SA from a sterile site (blood, joint fluid, tissue)
- Change in SA isolate susceptibilities to anti-staphylococcal antibiotics from baseline
- Change in SA isolate susceptibility to BAT from baseline; and
- Clinical and microbiological outcomes by foci of infection.

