### 3.1.2 Definition of Baseline

Baseline is defined as the last non-missing value prior to the first dose of study drug. If a subject was randomized but not treated, the baseline value is last non-missing value on or prior to randomization date. Baseline SAB is defined as SA isolated from positive blood culture within 72 hours prior to first dose of study treatment. Blood culture results are obtained from local microbiology laboratories.

Any eligibility protocol deviation from the 72-hour blood culture timepoint (relative to randomization) will be discussed and approved for individual subject inclusion in the per protocol MITT population before database lock.

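### The Phage-Sensitive ITT population is not tied to a pre-dose isolate, so S. aureus grown after dosing can help decide who is in it

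*SAP*

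**What the plan says.** The SAP (3.2.4) admits randomized subjects from both phases with at least 4 initial doses and "whose SA isolate is sensitive to at least 1 of the phage components that comprise the study drug". Protocol 9.1 is as silent on timing: "all randomized subjects who receive both BAT and study drug, and whose SA isolate is sensitive to at least 1 of the phage components". Neither says when the isolate must have been collected, or what happens when a subject has several isolates with different results.

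The only text that touches timing is SAP 3.3.3. It takes the base for counts and percentages as subjects with at least 4 doses "for whom the central laboratory received a blood SA isolate for phage sensitivity testing". It then explains who has such an isolate: "blood culture isolates based on blood culture samples from central laboratory (at screening, Day 1 to Day 7, TOC for study drug, TOC for BAT", continuing to EOS and unscheduled visits.

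Four other places matter:

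- SAP 3.1.2 does anchor the bacteremia criterion before dosing: "Baseline SAB is defined as SA isolated from positive blood culture within 72 hours prior to first dose of study treatment". That criterion serves the Per Protocol MITT population and is not carried over to this one.
- Protocol 7.7 states that "Isolates of SA from positive blood cultures for standard of care blood cultures used to assess eligibility as well as from study cultures" go to the central laboratory. Protocol 7.7.1 is weaker on the first isolate, which is sent "wherever possible, the isolate from the initial positive culture for SA".
- SAP 2.3.2 lists as an endpoint "Change in SA isolate sensitivity to AP-SA02 between initiation of study drug and the last isolation of SA from a sterile site".
- SAP 3.4 and 3.6 use this population for efficacy and pharmacodynamics only if needed, from a subject list that the Sponsor supplies. SAP 3.1.4 rules out formal testing, but SAP 3.4.1 gives chi-square p-values between arms.

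**The concern.** Phage sensitivity is used here to pick out the subjects in whom the drug could be expected to work. For the arms to stay comparable, that attribute has to be fixed before the first dose. Two routes let later events in.

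The first concerns who can be assessed. If no pre-dose isolate reached the central laboratory, a subject becomes assessable only by growing *S. aureus* after dosing. Early clearers are then left out, and persistent or relapsing subjects are kept.

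The second concerns how a subject is classified. The trial itself looks for a change in phage sensitivity on treatment, and only the active arm is exposed to phage. If a post-dose isolate decides the matter, an active subject who fails with a resistant isolate can be classed as not sensitive and leave the population. A placebo failure has no phage exposure to produce the same change.

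At stake is the comparison in one of the four efficacy populations that the SAP names.

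**Working it through.** **Inputs.** Phase 2a: about 42 randomized 2:1, so 28 active and 14 placebo; 90% expected in the MITT Population; 30% response on placebo and a 50-point difference (SAP 2.2.4). Product infects over 95% of clinical isolates (Protocol 1.1.3). Rates of emergent resistance and of missing pre-dose isolates are not given, so they are assumed below.

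**1. The plan's own figure.** 42 × 0.90 = 37.8, about 38, or 25:13. Exact enumeration of Fisher's test at 80% versus 30%, one-sided 0.05, gives 87.8% power, so the stated minimum of 80% holds. It applies to the MITT Population. No figure is stated for the Phage-Sensitive ITT, and nothing below rests on this one.

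**2. Exclusions expected on baseline isolates.** At 95% sensitive: 0.05 × 28 = 1.4 active and 0.05 × 14 = 0.7 placebo, 2.1 in all. The share is stated as over 95%, so the expected numbers are at most these.

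**3. What the missing rule would do.**

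| Central isolates | Earliest isolate, or any sensitive | Last isolate, or all sensitive |
|---|---|---|
| Pre-dose sensitive, post-dose resistant | in | out |
| No pre-dose, post-dose resistant | out | out |
| No pre-dose, post-dose sensitive | in | in |
| No pre-dose, no post-dose growth | not assessable | not assessable |

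The first row depends on a rule that the SAP does not state. The last three depend on post-dose growth whichever rule is chosen.

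**4. Losing active non-responders (assumed k).** Active rate = responders / (28 − k):

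| Responders | k=0 | k=1 | k=2 | k=3 | k=4 |
|---|---|---|---|---|---|
| 17 | 60.7% | 63.0% | 65.4% | 68.0% | 70.8% |
| 22 | 78.6% | 81.5% | 84.6% | 88.0% | 91.7% |

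**5. Losing clearers pulls the other way in the arm affected.** Suppose 20 of 28 active subjects respond (71.4%). Dropping 3 non-responders gives 20/25 = 80.0%. Dropping 3 responders who cleared early, with no pre-dose isolate, gives (20 − 3)/(28 − 3) = 17/25 = 68.0%. In placebo, 0.30 × 14 = 4.2, say 4/14 = 28.6%; losing one such responder gives 3/13 = 23.1%, which favours active. The net direction cannot be told in advance.

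**6. False findings in favour of active.** Assume equal true response in both arms (30%, 50%, 60% or 80%), 28:14, each active non-responder removed with probability f, and nobody removed from placebo. Exact enumeration, range over the four response rates:

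| f | Fisher, one-sided 0.05 | Chi-square, two-sided 0.05, favourable direction |
|---|---|---|
| 0 | 2.0–2.8% | 2.6–3.1% |
| 0.10 | 2.9–3.7% | 3.3–4.1% |
| 0.25 | 5.0–6.4% | 5.7–6.7% |
| 0.50 | 10.7–15.7% | 12.8–17.3% |

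The expected number removed is 28 × (1 − response rate) × f. At f = 0.25 that is 28 × 0.70 × 0.25 = 4.9 subjects at 30% response and 28 × 0.20 × 0.25 = 1.4 at 80%.

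**7. After the fix.** Membership fixed before dosing sets f = 0 for resistance that emerges on treatment. The first row of the last table then applies, and baseline exclusions fall on the same expected share of each arm.

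**The case against.** The strongest reply is that the sentence in SAP 3.3.3 sets a table denominator. It says who has a testable isolate, not which isolate decides sensitivity, and membership is defined in SAP 3.2.4. That is correct. A reader might infer that post-dose isolates do decide membership and that active failures with emergent resistance are removed. The documents do not support this: it needs a last-isolate or all-sensitive rule that is nowhere written, or a subject with no pre-dose isolate at the central laboratory.

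Such subjects should be few. Protocol 7.7 sends eligibility isolates centrally without qualification and plans two culture sets on Day 1 close to the start of dosing, unless cultures were already sent that day. Many clinical failures also could not be reclassified. Under Protocol 7.3, Table 2, death, new metastatic foci or persisting signs and symptoms count as no response without any positive post-dose blood culture. The move from 71.4% to 80.0% in step 5 is therefore an illustration, not a prediction.

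Nor would failures disappear from the trial: treated subjects stay in the ITT population, and change in sensitivity is reported as its own endpoint. The population already requires at least 4 doses, so it is a post-randomization subset in any case. The Sponsor may hold an operational rule in a document not seen here.

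These arguments limit the size of the problem. They do not remove it. SAP 3.3.3 expressly admits post-dose isolates, Protocol 7.7.1 does not guarantee the first isolate, and no tie-break rule makes the last three rows of the table in step 3 independent of what grows after dosing.

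**Conclusion.** The point holds as a gap that lets post-dose isolates affect membership, not as a demonstrated bias. The effect is probably small, since most subjects should have a pre-dose isolate at the central laboratory. Its net direction and size are unknown: losing active failures favours active, while losing clearers lowers the response rate of whichever arm loses them.

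In the one-directional worst case of step 6, the chance of a false finding for active changes little at f = 0.10, a little more than doubles at f = 0.25, and reaches 10.7–17.3% across the two tests at f = 0.50. These figures rest on assumed removal rates and an untouched placebo arm.

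The population is secondary, used only if needed and without formal testing, but it would still produce nominal p-values. SAP 3.3.3 summarizes reasons for exclusion for the Per Protocol MITT and PK populations but not for this one, and neither document says that its subject list must be fixed before unblinding. This is a cheap improvement.

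**What to change.** In SAP 3.2.4 and 3.3.3:

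- Define phage sensitivity by the last central-laboratory *S. aureus* blood isolate collected before the first dose. Judge this by collection date and time, because the Day 1 label alone does not show on which side of the first dose a culture fell.
- State a rule for discordant pre-dose isolates.
- Report subjects with no pre-dose isolate as baseline sensitivity unknown, by arm and outside the population, whatever grew later. Limit the 3.3.3 denominator to subjects with a pre-dose isolate.
- Use post-dose isolates only for the change-in-sensitivity endpoint.
- Fix the Sponsor's subject list before unblinding.

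The cost is SAP wording. SAP 3.6 already works with culture collection dates and times, so no new data are needed. The downside is a slightly smaller population where no pre-dose isolate reached the central laboratory.

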### 3.3.4 Demographic and Baseline Characteristics

Demographics and baseline characteristics will be summarized descriptively by Phase and treatment based on the randomized subjects.

The following demographic and baseline characteristics will be summarized:

- Age (Years)
- Age categories (<65 Years, ≥65 Years)
- Sex (Male, Female)
- Race (American Indian or Alaska Native, Asian, Black or African American, Native Hawaiian or Other Pacific Islander, White, Other)
- Ethnicity (Hispanic or Latino, Not Hispanic or Latino, Not Reported, Unknown)
- Height (cm)
- Weight (kg)
- Body mass index (kg/m^2)
- Modified Duke criteria (Major: Positive blood cultures for IE, Evidence of endocardial involvement; Minor: Predisposition, Fever, Vascular phenomena, Immunologic phenomena, Microbiologic evidence)
- Blood cultures positive for SA on Day -1 prior to study drug administration based on blood cultures tested by local microbiology laboratories
- Persistent SAB on 2 blood cultures obtained over 72 hours prior to study drug administration based on blood cultures tested by local microbiology laboratories
- Type of baseline SA from blood culture isolates based on blood cultures tested by local microbiology laboratories
  - MRSA
  - Methicillin-susceptible SA (MSSA)

- Unknown
- Randomized based on rapid testing (Yes, No)
- Signs/symptoms for focal site of SA infection (Pain at site of infection, Joint pain, Redness, etc.)
- Foci of SA infection at Screening (Head, Neck, Spine, Chest, etc.)
- Source control (Abscess drainage, Catheter or intravascular device removal, Washout of infected joint, Other)
- Adequacy of source control achieved by physician (Yes, No)
- Signs and symptoms of SAB at Screening (per protocol [section 7.3 of protocol](#))
  - Documented temperature  $\geq 38.0^{\circ}\text{C}$  ( $100.4^{\circ}\text{F}$ ) or  $\leq 36.0^{\circ}\text{C}$  ( $96.8^{\circ}\text{F}$ ) measured orally,  $\geq 38.5^{\circ}\text{C}$  ( $101.3^{\circ}\text{F}$ ) or  $\leq 36.5^{\circ}\text{C}$  ( $97.7^{\circ}\text{F}$ ) measured tympanically, or  $\geq 39^{\circ}\text{C}$  ( $102.2^{\circ}\text{F}$ ) or  $\leq 37^{\circ}\text{C}$  ( $98.6^{\circ}\text{F}$ ) measured rectally
  - Heart rate  $>90$  beats per minute
  - Respiratory rate  $>20$  breaths per minute
  - White blood cell count  $\geq 12.0 \times 10^9$  cells/L or  $\leq 0.4 \times 10^9$  cells/L, or  $\geq 10\%$  immature neutrophils
  - Systolic blood pressure  $<90$  mmHg; and/or
  - Pain associated with focal site of infection
- Time from first hospital admission to first dose of study drug received
- Time from first hospital admission to first BAT received (the time from first hospital admission to first BAT will not be calculable for those who received first BAT in the Emergency Department prior to hospital admission).

### 3.3.5 Medical History

Medical history will be coded to system organ class (SOC) and preferred term (PT) using the Medical Dictionary for Regulatory Activities (MedDRA). Counts and percentages of subjects with medical history by SOC and PT will be summarized by Phase and treatment based on the Safety Population.

All medical history data will be listed based on randomized subjects.

### 3.3.6 Prior and Concomitant Medications

Prior and concomitant medications will be coded to anatomical therapeutic chemical (ATC) class and PT using the World Health Organization (WHO) Drug Dictionary.

For summary purposes, medications will be considered prior medications if they stopped prior to the first dose of study drug, and concomitant medications if they were taken at any time after the first dose of study drug (i.e., started prior to the first dose of study drug and were ongoing, or started after the first dose of study drug).

Counts and percentages of subjects taking prior and concomitant medications by ATC class and PT will be summarized separately based on the Safety Population.

In addition, the BAT will be summarized with counts and percentages of subjects by ATC class and PT based on the Safety Population.

All prior and concomitant medications will be listed based on randomized subjects. A separate listing for BAT will be provided based on randomized subjects.

### 3.3.7 Study Drug Exposure

Days of exposure to study drug (days) will be calculated as:

- (Date/time of last dose of study drug – date/time of first dose of study drug)/3600/24

Within each dose, there are [REDACTED] phage types. For each phage type, compliance rate will be calculated as:

- Compliance (%) = (total number of PFUs administered / total number of PFUs planned)\*100
- Total number of PFUs administered = total number of phages administered \* planned PFUs
- Total number of PFUs planned = planned PFUs \* 20
- Total number of phages administered = total number of doses administered \* 1, since each dose has 1 phage for each phage type.

Total compliance considering [REDACTED] phage types in each dose is calculated as:

- Total compliance (%) = (total number of PFUs administered from [REDACTED] phage types / total number of PFUs planned from [REDACTED] phage types) \* 100
- Total number of PFUs administered from [REDACTED] phage types = total number of phages administered from [REDACTED] phage types \* planned PFUs
- Total number of PFUs planned from [REDACTED] phage types = planned PFUs \* 20 \* [REDACTED]
- Total number of phages administered from [REDACTED] phage types = total number of doses administered \* [REDACTED], since each dose has [REDACTED] phage types.

A dose with incomplete infusion will be assumed as a missed dose in compliance calculation for both compliance for each phage type and total compliance.

The following categories for study drug will be summarized:

- Descriptive statistics for days of exposure to study drug
- Descriptive statistics for the total number of doses administered
- Counts and percentages of subjects with at least one dose interruption
- Study drug compliance (%)

All study drug administration data will be listed based on randomized subjects.

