5.5 Drug Supplies

5.5.1 Formulation and Packaging

Study drug will be labeled according to local regulatory requirements.

Placebo will be a sterile dilution buffer used for active AP-SA02 [REDACTED]

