### 2.2 Study Design

#### 2.2.1 Overview

This is a first-in-human, prospective, Phase 1b/2a, randomized, double-blind, placebo-controlled, multiple ascending dose (MAD) study to assess the safety, tolerability, and efficacy of multiple IV doses of AP-SA02 as an adjunctive therapy to BAT and compared to BAT alone for the treatment of SAB. This multiple dose escalation design will assess the safety and tolerability, as well as the efficacy, of various dosing cohorts with phage pharmacokinetics (PK) to identify a dose and duration of dosing that offers the best therapeutic potential benefit.

In Phase 1b, a standard MAD design for safety and tolerability will begin by randomizing subjects in Phase 1b Cohort 1 to receive either approximately  $2 \times 10^9$  plaque-forming units (PFU) or placebo in addition to BAT. A Data Review Committee (DRC) will convene to review the data from Phase 1b Cohorts and during Phase 2a, as needed. The DRC will review emerging safety data throughout the study to determine if it is safe and appropriate to continue the study with the currently planned dose levels for the subsequent cohorts, or if further refinement of the proposed dose levels or dosing duration is warranted. The planned dose levels and dosing duration after Phase 1b Cohort 1 may be modified and/or additional cohorts may be added based on emerging information from the current study as well as other ongoing studies. The highest total daily dose will not exceed  $8 \times 10^{11}$  PFU and no more than 40 additional subjects will be added without a protocol amendment. The DRC will also determine how to advance the cohorts (serially or simultaneously). The DRC can receive unblinded data, if requested and deemed necessary to adequately complete their review. Further details regarding the role, responsibilities, and procedures of the DRC will be provided in the DRC Charter.

The planned enrollment in each of the Phase 1b cohorts is 4 subjects per cohort (AP-SA02 to placebo 3:1); however, this may be modified after DRC review. Subjects in Phase 1b Cohort 1 will receive IV bolus infusion doses of blinded study drug every 6 hours for 5 study days (a total of 20 doses) in an inpatient location in addition to BAT. Following 5 days of dosing with study drug, additional study visits will be conducted at the End of Treatment (EOT) for study drug (Day 5), at the Test of Cure (TOC) for

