study drug (Day 12), TOC for BAT (7 days [ $\pm 1$  day] after the end of BAT), and at End of Study (EOS) (28 days after the end of BAT). Subsequent cohorts (e.g., planned Phase 1b Cohort 2 or additional cohorts [up to 3]) will proceed similarly; however, the duration of dosing may be modified after the DRC review of the preceding cohort.

Study procedures will follow the Schedule of Procedures ([Appendix A](#)).

In Phase 2a, approximately 42 subjects will receive IV bolus infusion doses of blinded study drug every 6 hours, for no more than 14 days as determined by analysis during or after Phase 1b, in addition to BAT. Following 5 days of dosing with study drug, additional study visits will be conducted at EOT for study drug (Day 5), TOC for study drug (Day 12), TOC for BAT (7 days [ $\pm 1$  day] after the end of BAT), and EOS (28 days after the end of BAT). If the study drug EOT is extended after the DRC review, the study drug TOC visit will occur 7 days after the last day of dosing and the study drug EOS visit will occur 28 days after the end of BAT.

The following dose cohorts are planned:

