#### Phase 2a

- Phase 2a (AP-SA02 to placebo 2:1):
  - Dose and duration are to be determined based on safety and tolerability from or after Phase 1b, administered via IV bolus infusion.

Note: The dose, frequency, and duration may be modified after DRC review. Maximum dosing duration will be no more than 14 days.

A DRC will be convened to review all blinded safety data through TOC for study drug (Day 12) to recommend dose escalation. Safety stopping rules, including the number of dose-limiting toxicities, are prespecified in [Section 4.3 of protocol](#). The DRC can receive unblinded data, if requested and deemed necessary to adequately complete their review. Upon completion of Phase 1b Cohort 2, Phase 2a may be initiated and may be an expansion of one of the previous cohorts.

In Phase 2a, subjects will be randomized in a 2:1 ratio to receive AP-SA02 or placebo. Randomization will be stratified by methicillin susceptibility/resistance. Subjects will be on BAT for a minimum of 28 days to 56 days (complicated SAB) and followed through 28 days after the end of BAT, for a total of 56 to 84 days in the study. The BAT must be planned for a minimum of 28 days and a maximum of 56 days, inclusive of the days on BAT started prior to study enrollment/randomization. The EOT for BAT will be defined based on the prespecified duration of therapy at the time of enrollment. The prespecified duration

of BAT at Screening may be increased within 7 days after randomization with duration of BAT no more than 56 days in the event that new/additional clinical information warrants a longer duration of therapy; this must be documented in the subject's source chart and electronic case report form (eCRF). All changes made to the subject's BAT and the reason for such changes must be documented on the appropriate eCRF.

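### SAP 3.3.7 reports a complete 5-day course as 4.75 days of exposure and a single dose as 0 days; its compliance formula has no placebo rule and a dose count fixed at 20.

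*SAP*

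**What the plan says.** SAP 3.3.7 (Study Drug Exposure) gives two calculations.

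- **Days of exposure:** "Date/time of last dose of study drug – date/time of first dose of study drug)/3600/24". Nothing is added for the last dose.
- **Compliance, per phage type:** PFUs administered as a percentage of PFUs planned. The numerator is "Total number of PFUs administered = total number of phages administered \* planned PFUs", where "Total number of phages administered = total number of doses administered \* 1, since each dose has 1 phage for each phage type". The denominator is "Total number of PFUs planned = planned PFUs \* 20". A total across phage types is built the same way. A dose with an incomplete infusion counts as missed.

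The section goes on to plan descriptive summaries of days of exposure, number of doses and compliance for study drug. It has no separate rule for placebo.

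Other places bear on these formulas:

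- SAP 2.2.1 sets the Phase 1b Cohort 1 course at "every 6 hours for 5 study days (a total of 20 doses".
- For Phase 2a, SAP 2.2.1 has dosing "every 6 hours, for no more than 14 days as determined by analysis during or after Phase 1b", and its Phase 2a note adds: "The dose, frequency, and duration may be modified after DRC review". Footnote ii of SAP Appendix A repeats that option.
- SAP 2.2.3 states 5 consecutive days and does not mention the option.
- Protocol 5.5.1: "Placebo will be a sterile dilution buffer used for active AP-SA02".

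**The concern.** The label promises days of exposure, but the formula returns the interval between two infusions. The shortfall is always one dosing interval, so in relative terms it is largest for subjects who stopped early, who are of particular interest in a first-in-human safety review. The Safety Population (SAP 3.2.5) admits anyone who had at least one dose, so a dosed subject can enter the exposure table with a value of zero. The SAP's date-based time-to-event formulas (3.4.1) add 1, so an event on the first dosing day counts as day 1 there, while a subject with one dose has 0 days here.

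For compliance, study drug means phage or placebo, yet the only formula is in units that a buffer would not be expected to contain. A programmer has to decide what planned PFU means for placebo. The factor 20 is written as a constant in a plan that elsewhere allows the number of doses to change.

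What is at stake is whether the exposure and compliance tables in the study report can be read at face value.

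**Working it through.** **Inputs**

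- Dosing every 6 hours for 5 days (SAP 2.2.1; Protocol 5.1, Table 1; Protocol 5.5.3).
- Exposure and compliance formulas (SAP 3.3.7).
- Maximum duration 14 days (SAP 2.2.1).
- Phase 2a: about 42 subjects randomized 2:1 (SAP 2.2.1, 2.2.4).
- Planned PFU for placebo: not stated in the documents.

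**1. The plan's own figure.** Doses per day = 24/6 = 4, and 4 × 5 = 20 doses. The factor 20 is reproduced. Table 1 of the protocol agrees: 2 × 10^9 × 4 × 5 = 4 × 10^10 PFU for Cohort 1, and 2 × 10^10 × 4 × 5 = 4 × 10^11 PFU for Cohort 2.

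**2. Exposure.** With n on-time doses there are n − 1 intervals, so the formula returns (n − 1) × 6/24 days. With one interval added it would return n × 6/24.

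| Doses | As written (days) | One interval added (days) | Understatement |
|---|---|---|---|
| 1 | 0 | 0.25 | 0.25/0.25 = 100% |
| 4 | 0.75 | 1.00 | 0.25/1.00 = 25% |
| 10 | 2.25 | 2.50 | 0.25/2.50 = 10% |
| 20 | 4.75 | 5.00 | 0.25/5.00 = 5% |

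These values assume on-time dosing. Under Protocol 5.5.3 a dose delayed by more than 2 hours moves all later doses. Three 3-hour shifts, for example, give (19 × 6 + 9)/24 = 5.125 days as written.

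**3. Compliance on the planned course.** With planned PFU = P > 0, compliance = 100 × (n × P)/(P × 20) = 100 × n/20. P cancels, as does the number of phage types in the total. So 20 doses give 100%, 19 give 95% and 18 give 90%. Rescheduled doses do not disturb this, because Protocol 5.5.3 has subjects receive all doses and the count stays at 20.

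**4. Placebo.** If planned PFU is set to 0, the ratio is 0/(0 × 20), which is undefined. In Phase 2a that would concern about 42/3 = 14 subjects. If any positive nominal value is used, compliance is n/20, as in the active arm.

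**5. Changed schedule.** With the denominator held at 20, complete six-hourly courses would score:

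- 6 days: 24/20 = 120%
- 7 days: 28/20 = 140%
- 14 days: 56/20 = 280%

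A complete 5-day course at a lower frequency would score below 100%. As arithmetic illustrations only, 15 doses give 15/20 = 75% and 10 doses give 10/20 = 50%.

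**The case against.** The case that little is wrong has four parts.

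- **Exposure is partly a matter of convention.** 4.75 days is the true time from first to last infusion, and adding an interval is only one way to count. This stands as far as it goes, but the quantity is not labelled as elapsed time, and 0 days of exposure for a dosed subject is hard to defend under any label that includes the word exposure.
- **Placebo compliance need not fail.** A reader might infer that every placebo subject scores 0/0 and that compliance cannot be compared between arms. The documents do not support that. They give no planned PFU for placebo, and the description of placebo is partly redacted. Any nominal value cancels, and the number of doses, summarized in the same section, works identically in both arms. What remains is that the SAP leaves the rule unstated.
- **The factor 20 is right for the planned course** and agrees with SAP 2.2.3. A reader might infer that compliance above 100% will appear in this trial. Nothing in the documents shows that dosing was extended or its frequency changed, so 280% is a ceiling under an option the plan keeps open.
- **The consequences are small.** A reader might infer that safety rates are distorted. They are not: SAP 3.7.1 summarizes adverse events as counts and percentages of subjects, with no exposure-adjusted rate. The populations that require 4 doses (SAP 3.2.2 to 3.2.4) count doses directly. SAP 2.3.2 lists an exposure-response endpoint but does not tie it to the formulas in 3.3.7. A subject who had one dose would also remain visible in the dose counts and listings. This part stands in full.

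**Conclusion.** The exposure formula gives a misleading value whenever it is read as its label says: 4.75 days for an on-time 5-day course, 0.75 days for 4 doses and 0 days for one dose. This follows directly from the text and assumes only on-time six-hourly dosing.

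The compliance formula is correct for an active-arm subject on the planned 20-dose course. It has two gaps, both conditional. It states no placebo rule, and is undefined for that arm if placebo's planned PFU is taken as 0. Its denominator also does not follow the changes of frequency or duration that SAP 2.2.1 and Appendix A allow, with 280% as the extreme for a complete six-hourly 14-day course.

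It would go too far to say that the formulas are wrong throughout, or that safety or efficacy conclusions depend on them. The effect is confined to the descriptive exposure and compliance summaries. The correction is still worth making before database lock, because those tables are where a reader of a first-in-human trial looks to see how much drug subjects received.

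**What to change.** 1. **Exposure.** Add one planned dosing interval: (last dose time − first dose time + 6 hours, or the interval in force if modified)/24 hours. This gives 5.00 days for 20 on-time doses and 0.25 days for one. There are two alternatives. One is date of last dose − date of first dose + 1, in line with the SAP's date-based formulas. It gives 1 day for one dose, but 5 or 6 calendar days for 20 on-time doses, depending on whether the first dose falls before 06:00. The other is to keep the formula and relabel it as time from first to last dose.
2. **Compliance.** Define it in both arms as 100 × complete doses administered / doses planned for that subject's cohort. Keep the existing rule that an incomplete infusion counts as missed. A complete course then scores 100% whatever its length (20/20, 28/28, 56/56). Report PFU totals for the active arm only.
3. **Consistency.** Reconcile SAP 2.2.3, which gives 5 days without exception, with SAP 2.2.1 and footnote ii of SAP Appendix A, which allow modification after DRC review.

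The cost is SAP wording and two lines of programming. No new data are needed.
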